## 9. Potential Risks

The magnetic twitch assessment procedures described in the protocol have been used extensively in both the US and England. We have performed this assessment many times in our ICU population over the past year both to recruit patients into other studies and to perform diagnostic studies on ICU patients for routine management issues (i.e. to detect diaphragm paralysis, to assess the response to treatment for myasthenia and other neuromuscular diseases, to assess patients with respiratory failure of unclear etiology). We have not had a single complication from our use of magnetic stimulation per se or from placement of esophageal and gastric balloon tipped catheters for pressure assessment. In addition, the PI recently visited [name] and [name] laboratories in England and spoke directly with them regarding their experience with the magnetic twitch-Pdi technique. They have not observed a serious complication from this procedure and reported only minor temporary discomfort from the delivery of the magnetic stimulus or from placement of the esophageal and gastric balloons. There is no reported long term risk reported in response to single stimulus excitation of peripheral nerves (such as the phrenic nerve) using a magnetic stimulating device. The magnetic stimulator to be employed (Magstim 200) is commonly used for the application proposed and is FDA approved for stimulation of peripheral nerves.

We extensively searched the Internet and other sources and, to our knowledge, hydroxymethylbutyrate (HMB) has no known side effects at any dosage. This agent is a biopharmaceutical, a normal breakdown product of leucine, and is present in small quantities in all human beings. The other agent to be employed in the present study, eicosapentaenoic acid (EPA) has only been reported to produce minor side effects (occasional nausea, diarrhea, heartburn, skin rash, itching) at the dosage to be employed in the current study. At high doses this agent may potentiate the effects of Coumadin or interfere with platelet function; for this reason we will not use doses higher than the one included in the study protocol. Both drugs are available as over the counter medicines and are not subject to FDA regulation.

Risks associated with biopsy of the vastus lateralis muscle include bleeding into the biopsy site and potential infection at the site. There should be no risks associated with measurement of muscle size via ultrasound or chart review to assess clinical parameters. As indicated in the above paragraphs most of procedures included in this study are extremely safe, with no possibility of patient injury due to ultrasound measurement, magnetic stimulation or HMB administration. In addition, it is difficult to imagine that the low dose of EPA to be used will produce significant injury. The only component of the experimental plan that could potentially cause patient injury is the

vastus lateralis biopsy. If the investigators detect problems as a result of the biopsy, or if the family or professionals caring for the patient complain of biopsy complications or report other possible complications that result from these studies, we will stop experimentation, and the patient will be withdrawn from the study.

#### 10. Safety Precautions.

To minimize the risk of bleeding from balloon placement, patients with variceal bleeds will be excluded from this study. Because assessment of PdiTw involves transient removal from mechanical ventilation, patients requiring high levels of PEEP, high levels of oxygen or in severe shock will be excluded from study. As indicated in above paragraphs, these procedures have been extensively employed in London, UK to evaluate patients in both outpatient and ICU settings and the investigators there have not observed complications with either balloon placement or magnetic stimulation. In fact there are no reported adverse effects using magnetic stimulation to assess peripheral nerves except for an isolated report of interference with pacemaker function in one patient. For this reason, we will also exclude patients with pacemakers from this study. As per standard ICU protocols at UK, during all measurements all patients will be connected to invasive or non-invasive blood pressure transducers, EKG monitors, and pulse oximetry monitors, providing a continuous assessment of patient pulse rate, blood pressure, and oxygen saturation during assessments. If desaturation to less than 90%, a raise in heart rate by more than 20 beats, a rise in mean blood pressure more than 10 torr or a fall in mean blood pressure of more than 10 torr is noted, measurements will stop. The PI will return at 24 hours after each study to the patient's bedside to ascertain if any untoward events have occurred and to elicit feedback regarding any concerns that the patient and/or their family and/or the nursing staff caring for the patient may have. If problems are encountered they will be reported to the IRB and data monitoring board.

To minimize the risk that the patient's privacy would be compromised, all data will be placed into a file at the conclusion of the bedside study and this file will be placed into a locked file cabinet in the office of the PI. Each file will be assigned a research number, and all data abstracted from the file of an individual subject will be referred to in later data analysis by this patient file number with no reference to any identifiable patient characteristics (e.g. name, SS number, hospital number). The mean data for the study will also be placed in a mean data file and this information also kept in the locked file drawer in the PI's office.

#### 11. Benefit vs. Risk.

Based on our previous experience and the reported experiences of others, we believe the major stress that will be felt by subjects will be the discomfort associated with balloon-tipped catheter placement into the esophagus as well as the momentary sensation associated with magnetic stimulation. The sensation associated with magnetic stimulation is not painful but is more like a "jolt" related to the sudden involuntary contraction of the muscles being stimulated distal to the nerve. We do not believe these techniques pose a significant risk to patients, in that no long term adverse consequences should occur providing the exclusion criteria used for this study are rigorously followed.

Neither of the drugs to be used (HMB or EPA) has been reported to cause side effects at the dosages chosen. In fact, we did not find report of any side effects from these doses of HMB. EPA has been reported to cause minor side effects in occasional patients (nausea; diarrhea, heartburn, skin rash, itching, and joint, back, and muscle pain). Both agents are over the counter agents that are sold as health food supplements and are available without prescription. Neither is an FDA regulated substance.

Patients randomized to drug treatment (HMB and/or EPA) may well be stronger as a result of this treatment and may well have a shortened ICU stay, a lower mortality, and less long term morbidity (i.e. better ambulation, less dyspnea). There are, however, important potential benefits for the patients taking part in this study. To date, our work in the ICU indicates that the average twitch transdiaphragmatic pressure generated by ICU patients is only 23% of the value seen in normal healthy adults. In animal studies, both HMB and EPA have been shown to preserve diaphragm strength in models of critical illness. If these drugs also prove effective in preserving or improving diaphragm strength in ICU patients, the patients randomized to receive these agents may be able to recover from respiratory failure faster and be weaned from mechanical ventilation sooner than control patients receiving control solutions.

#### 12. Available Alternative Treatments.

Currently, there is no defined drug treatment to prevent or reverse the development of weakness in critically ill patients. As a result, there is no acceptable alternative to the clinical trial drugs (HMB, EPA) planned for these studies. While one might think that androgens would be an acceptable alternative, a recent study found these agents worsen lung function and actually had deleterious effects on outcomes when tested in surgical ICU patients. Currently there are no drugs that have been identified that can improve respiratory muscle strength in critically ill patients. As a result, there are no alternative treatments to replace the agents being studied in the current project.

#### 13. Research Materials, Records, Privacy.

All data collected from the study (i.e. tracings of pressure measurements, demographic/clinical data obtained from chart review, the survey form filled out by the attending physician) will be placed in a folder which will be stored in a locked filing cabinet in the office of the principal investigator in MN616. None of this information will be shared with other investigators. All folders will be given a study number and further analysis of mean data obtained from patient study folders will be carried out with only the patient study number as identification. Folders containing mean data will also be stored in the locked filing cabinet in MN616.

#### 14. Confidentiality.

For publication, no individual identifying features of the patients will be included in abstracts and papers generated using the data collected in this study. As indicated in section 13, all records will be kept in a locked file cabinet in the PI's office. The records for this study will be kept until seven years after the data is published, in keeping with current NIH recommendations on data archiving. The data will be kept in the locked file cabinet in MN616 at least until the data is published and then transferred to a second locked archival filing cabinet in the PI's office. At seven years after publication all data

will be destroyed by shredding the documents. All data collected from the study (e.g. pressure, force, and muscle size measurements, demographic/clinical data obtained from chart review) for a given patient will be placed in a folder which will be stored in a locked filing cabinet in the office of the principal investigator in MN616. All folders will be given a study number and further analysis of mean data obtained from patient study folders will be carried out with only the patient study number as identification. Folders containing mean data will also be stored in a locked filing cabinet in MN616 of Chandler Medical Center, University of Kentucky. For publication, no individual identifying features of the patients will be included in abstracts and papers generated using the data collected in this study.

#### 15. Payment.

No subject will be paid for participation in the study.

#### 16. Costs to Subjects.

There will be no cost to subjects for participation in the study.

#### 17A. Data Monitoring: Data Safety Monitoring Board

A detailed description of our Data Safety Monitoring Plan is attached. In brief, to monitor the long term conduct of the study, including monitoring of adverse effects, we will employ the study monitoring board provided by the CCTS at the University of Kentucky. This board will include the chair, [name], [name], and other current members of the DSMB.

Monitoring for adverse events will be conducted in real-time by the study investigators and study coordinator. Risks involved with this study are considered greater than minimal risk. For this reason, we will utilize the standing independent Data Safety Monitoring Board (DSMB) as chartered by the University of Kentucky Center for Clinical and Translational Science (CCTS) to monitor the safety of the study.

The DSMB will meet three times a year and will review subject recruitment, adverse effects, side effects, laboratory results, withdrawals, protocol violations, and inclusion/exclusion criteria. More frequent meetings will take place if necessary. The board will compile a report for each meeting and present their findings to the PI.

We will also have the DSMB provide the recommendations they send to us to the NHLBI. We will also provide the NHLBI with the meeting dates of the DSMB. The NIH will also be notified of all adverse effects and will have our SAE form send to her along with the safety officer, the IRB and the DSMB.

#### 17B. Safety Monitoring

During the execution of this protocol the nurse assigned to the patient will be asked to be present in the room to provide an ongoing assessment of patient vital signs. As per standard ICU protocols at UK, during all measurements all patients will be connected to invasive or non-invasive blood pressure transducers, EKG monitors, and pulse oximetry monitors, providing a continuous assessment of patient pulse rate, blood pressure, and oxygen saturation. If desaturation to less than 90%, a raise in heart rate by more than 20 beats, a rise in mean blood pressure more than 10 torr or a fall in mean blood pressure of more than 10 torr is noted, measurements will stop and the patient will be

returned to mechanical ventilation. As per standard ICU protocols at UK, during all measurements all patients will be connected to invasive or non-invasive blood pressure transducers, EKG monitors, and pulse oximetry monitors, providing a continuous assessment of patient pulse rate, blood pressure, and oxygen saturation during assessments. If desaturation to less than 90%, a raise in heart rate by more than 20 beats, a rise in mean blood pressure more than 10 torr or a fall in mean blood pressure of more than 10 torr is noted, measurements will stop. The PI will return at 24 hours after each study to the patient's bedside to ascertain if any untoward events have occurred and to elicit feedback regarding any concerns that the patient and/or their family and/or the nursing staff caring for the patient may have. If problems are encountered they will be reported to the IRB and data monitoring board. The PI or [name] will also return to inspect the muscle biopsy site daily for seven days to confirm adequate healing at the site.

The PI will provide the nurse with his cell phone number at the completion of each data collection with instructions to call the PI if any untoward events occur within the following 24 hours. In addition, the PI will return at 24 hours after each study to the patient's bedside to ascertain if any untoward events have occurred and to elicit feedback regarding any concerns that the patient and/or their family and/or the nursing staff caring for the patient may have. If problems are encountered they will be reported to both the monitoring board described in the preceding section and to the IRB board by the PI.

#### 18. Subject Complaints.

After obtaining consent, the patient and his family will be given a sheet providing the office number, paging number, and cell phone for the PI and instructions on how to contact the PI. We will provide the patient and his family any information obtained from the Pimax and Pdi-twitch measurements, and will provide them with information as to whether the measured numbers are normal or reduced. If any complaints are registered by a subject these will be recorded and placed in the patient's study file. This information will be handled in a confidential matter (see above).

#### 19. Research With Non-English Speaking or Foreign Cultures:

We do not plan to study patients that, because of language barriers, cannot understand English. This study is too complicated to be dealt with adequately through interpreters.

#### 20. HIV Research:

This is not applicable.

#### 21. FDA Regulated Research:

This is not applicable.

**Effect of EPA and HMB on Strength in ICU Patients**

**NCT01270516**

**3-12-21**

**Statistical Analysis**

## Statistical Analysis

Non-parametric ANOVA testing was used to compare variables (e.g. changes in diaphragm twitch) across the four experimental groups, with post-hoc testing (Tukeys) to determine significance of differences. A p value of less than 0.05 was taken as indicating statistical significance for comparisons.

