**Effect of EPA and HMB on Strength in ICU Patients**

**NCT01270516**

**3-12-21**

**Research Description**

## **Form B: Research Description**

### **1. Background.**

Over the past 20 years there has been a dramatic growth in the numbers of patients requiring mechanical ventilation to sustain life in the United States. At most large medical centers, the number of patients needing more than transient mechanical ventilation for respiratory insufficiency has approximately tripled over the past 10 years. To deal with this burgeoning number of mechanically ventilated patients, stand-alone ventilator units have been created in the United States in most large cities, with literally hundreds of mechanically ventilated patients placed in such units in each of the large metropolitan areas in this country. In aggregate, we estimate that as many as 50,000 patients are on sustained mechanical ventilation at any given time in the United States. The total cost of caring for these patients now consumes approximately 6% of the yearly health care budget, or upwards of 1% of the United States GNP.

We have recently completed a study at the University of Kentucky that indicates that a major process contributing to respiratory failure in critically ill patients is respiratory muscle weakness. This work found that the average patient in the UK ICU has a diaphragm pressure generation (PDI) in response to phrenic magnetic twitch stimulation of only  $8 \pm 3$  cm H2O, compared to an accepted normal value of 30 cm H2O for healthy adults. Moreover, we found that 70% of patients have twitch PDI measurements that are less than a third of normal. These data suggest, moreover, that severe respiratory muscle weakness contributes to respiratory failure in mechanically ventilated patients, with the weakest patients taking the longest to wean from mechanical ventilation and having the highest mortality.

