## 2. Objectives.

The objective for this study is to determine if administration of either EPA or HMB can prevent or reverse the development of respiratory muscle weakness in critically ill, mechanically ventilated patients. We plan to randomize patients accepted into this protocol to administration of either a control (saline enteral control solution), EPA administration, HMB, or the combination of EPA +HMB. Drugs will be administered for 10 days and measurements of muscle strength (diaphragm and quadriceps), muscle size (diaphragm and quadriceps thickness by ultrasound), and muscle signaling protein profile (obtained using vastus lateralis muscle biopsy specimens) will be performed immediately before and immediately after the period of drug administration (days 1 and 11). An additional assessment of muscle strength, muscle size and signaling protein profile will be made at 10 days after completion of the drug administration regimen (i.e. on day 21). As part of the study, patients will be weaned from mechanical ventilation using the University of Kentucky ventilator separation protocol, the nutritional regimen will be reviewed with the MICU nutritionists to ensure it conforms to study requirements, and it is expected that patients will receive standard MICU mobilization therapy by physical therapy.

We will also perform a chart review and assess ventilator mechanics (respiratory system static compliance and inspiratory airway resistance) at the time of strength assessment. We would expect that mean diaphragm and quadriceps muscle strength and size measurements will be similar for four groups immediately before initiation of drug administration. Our hypothesis will be supported if post drug administration diaphragm and limb muscle strength are higher for patients receiving EPA , HMB and/or the combination of EPA+HMB when compared the control group receiving no active drug. We will also determine if administration of these agents shortens the time required to wean patients from mechanical ventilation.

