### Trial arm sizes.

Control	EPA	HMB	HMB+EPA	Total
20	17	18	18	73

Some specific measurements were not possible due to patient refusal, patient transfer, or care withdrawal by the attending physician. Therefore, besides providing sample medians (interquartile ranges), sample sizes (n) are also given in the following table of descriptive statistics and p-values testing for differences between the 4 trial arms:

Location	Variable	Control	EPA	HMB	HMB+EPA	p-value
Diaphragm	Force after treatment	5.7 (3.7, 8.0) n=13	5.4 (3.5, 6.7) n=10	4.0 (3.5, 6.0) n=9	6.0 (3.9, 8.3) n=12	0.63
	Change in force	1.3 (0.0, 1.7) n=13	0.1 (-1.4, 3.2) n=10	1.5 (0.0, 3.2) n=9	0.7 (-1.8, 3.7) n=12	0.93
	% change in force	19 (0, 40) n=13	2 (-35, 128) n=10	58 (0, 75) n=9	19 (-24, 100) n=12	0.87
	% change in size	5.0 (0.0, 8.0) n=15	5.0 (0.0, 11.0) n=11	6.0 (0.0, 11.0) n=12	3.0 (-5.5, 16.0) n=12	0.97
Quadriceps	Force after treatment	4.6 (1.8, 11.6) n=17	3.4 (1.7, 11.0) n=13	4.0 (1.0, 9.5) n=11	4.6 (1.5, 6.5) n=13	0.80
	Change in force	1.0 (0.1, 3.7) n=17	0.3 (-0.4, 2.4) n=13	0.5 (-5.0, 3.2) n=11	0.1 (-1.1, 2.2) n=13	0.57
	% change in force	61 (0, 125) n=17	18 (-28, 62) n=13	51 (-50, 118) n=11	6 (-42, 63) n=13	0.72
	% change in size	1.0 (-14.0, 15.0) n=17	-6.0 (-17.0, -1.0) n=13	-12.0 (-23.0, 6.0) n=11	4.0 (-14.5, 14.0) n=13	0.35

Changes are from before to after treatment.

Median (interquartile range) is presented instead of mean (standard deviation) due to outliers.

p-values come from Kruskal-Wallis tests, the non-parametric alternative to one-way ANOVA

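### The hypothesis compares each active arm with control, but the SAP reports no estimate or interval for any such contrast, so its null p-values do not show absence of effect

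*SAP*

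**What the plan says.** Protocol section 2 (Objectives) states what would support the hypothesis, for both muscle groups once treatment has ended: "strength are higher for patients receiving EPA , HMB and/or the combination of EPA+HMB when compared the control group receiving no active drug". That is three contrasts, each against control.

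The SAP's opening section describes the main test as follows: "Non-parametric ANOVA testing was used to compare variables (e.g. changes in diaphragm twitch) across the four experimental groups". For the follow-up comparisons it says only this: "with post-hoc testing (Tukeys) to determine significance of differences". On the threshold it adds: "A p value of less than 0.05 was taken as indicating statistical significance for comparisons".

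Under "Trial arm sizes", the SAP introduces its table as "descriptive statistics and p-values testing for differences between the 4 trial arms". One footnote explains the tests: "p-values come from Kruskal-Wallis tests, the non-parametric alternative to one-way ANOVA". Another explains the summary statistics: "Median (interquartile range) is presented instead of mean (standard deviation) due to outliers". Each of the eight rows has four medians with interquartile ranges, four sample sizes and one p-value. Neither document gives an active-minus-control difference, a confidence interval or a pairwise result.

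**The concern.** A Kruskal-Wallis test across four arms has no direction and yields no effect size. It asks whether the arms differ in any way, whereas the protocol asks whether each active arm beats control. A p of 0.63 (diaphragm force after treatment) or 0.93 (change in diaphragm force) says nothing about how large a benefit or harm against control is still compatible with the data.

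With 9 to 13 patients per arm contributing diaphragm force, that range could be wide. A reader who sees only the p-values may conclude that the supplements do nothing. The quartiles let a reader subtract medians, but an interval cannot be had from them without assuming a distribution. The sponsor holds the patient data and can give the interval directly.

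**Working it through.** **1. The plan's own figures.** The p-values cannot be reproduced exactly without patient data. As a consistency check, samples were built to match each arm's median, quartiles and n, and Kruskal-Wallis was run on them. Diaphragm force after treatment gave 0.70 (SAP 0.63) and change in diaphragm force gave 0.88 (SAP 0.93). All eight rows are non-significant both ways, so nothing suggests that the reported p-values are wrong.

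**2. Inputs.** SAP table, diaphragm rows, n = 13 (control), 10 (EPA), 9 (HMB), 12 (combination). The total is 13 + 10 + 9 + 12 = 44 of 73 (60%). The table gives no units.

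**3. Arm SDs.** SD = interquartile range / 1.349, which assumes normality.

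| Row | Control | EPA | HMB | Combination |
|---|---|---|---|---|
| Force after: range | 4.3 | 3.2 | 2.5 | 4.4 |
| Force after: SD | 3.19 | 2.37 | 1.85 | 3.26 |
| Change: range | 1.7 | 4.6 | 3.2 | 5.5 |
| Change: SD | 1.26 | 3.41 | 2.37 | 4.08 |

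**4. Differences in medians, active minus control.**
- Force after: EPA 5.4 - 5.7 = -0.3; HMB 4.0 - 5.7 = -1.7; combination 6.0 - 5.7 = +0.3.
- Change: EPA 0.1 - 1.3 = -1.2; HMB 1.5 - 1.3 = +0.2; combination 0.7 - 1.3 = -0.6.

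**5. Expected Hodges-Lehmann interval.** The limits are order statistics of all pairwise differences, with the rank taken from the exact Mann-Whitney distribution. The half-width is the average over 20,000 simulated normal trials per contrast with the arm SDs above. Each interval is centred on the difference in medians.

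| Contrast | Half-width, 95% | 95% interval | Half-width, 98.3% | 98.3% interval |
|---|---|---|---|---|
| Force after, EPA | 2.5 | -2.8 to +2.2 | 3.2 | -3.5 to +2.9 |
| Force after, HMB | 2.5 | -4.2 to +0.8 | 3.1 | -4.8 to +1.4 |
| Force after, combination | 2.8 | -2.5 to +3.1 | 3.4 | -3.1 to +3.7 |
| Change, EPA | 2.3 | -3.5 to +1.1 | 2.9 | -4.1 to +1.7 |
| Change, HMB | 1.8 | -1.6 to +2.0 | 2.3 | -2.1 to +2.5 |
| Change, combination | 2.6 | -3.2 to +2.0 | 3.2 | -3.8 to +2.6 |

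The 98.3% level is 1 - 0.05/3, the Bonferroni level for three contrasts in a row.

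**6. Why arm-specific SDs.** A pooled SD (2.97 for change) gives a half-width of 2.8 for the HMB change contrast, against 1.8 with the arms' own SDs. The spreads differ too much to pool.

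**7. Coverage.** With the arm SDs for change in diaphragm force, a nominal 95% Hodges-Lehmann interval covers about 92% to 94%. Three 98.3% intervals jointly cover about 92%, against about 96% with equal spread.

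**8. Quadriceps.** Control force after treatment is 4.6 (1.8, 11.6). The upper quartile is 7.0 above the median and the lower quartile only 2.8 below it. The implied SD is 9.8/1.349 = 7.26, which would put one SD below the median at 4.6 - 7.26 = -2.7, an impossible force. The approximation is not usable there. The diaphragm rows are not symmetric either (control change 1.3, quartiles 0.0 and 1.7), so steps 5 and 7 are rough.

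**The case against.** The strongest reply is that this is a matter of reporting. The documented test was run, its p-values are credible, and medians, quartiles and n are all shown, so a reader can see that the differences are small or inconsistent in direction. This largely stands: the added estimates are not expected to make anything significant.

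Three further objections also stand, and they limit the point.

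- **Missing Tukey results.** A reader might infer that a promised analysis was withheld, or that the hypothesis could not be tested. The documents support neither. Every omnibus p is at least 0.35, so post-hoc tests may simply not have been triggered, although the SAP does not say so. Three of Tukey's six pairs are the control contrasts.
- **No yardstick.** A reader might infer that the trial failed to exclude an important benefit. For scale, +3.1 is 3.1/5.7 = 54% of the control median, but neither document names a target difference or margin.
- **Incomplete measurement.** Only 44 of 73 patients have diaphragm force data. The SAP attributes gaps to refusals, transfers and withdrawal of care, which may be related to outcome. A reader might take the intervals as limits on the effect in everyone randomised, which they are not.

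What the reply does not answer is that the contrasts named in the hypothesis have no estimate and no interval, and a p-value cannot supply either.

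**Conclusion.** The point holds as a gap in estimation. It is not an error in the tests. The SAP's null result comes with no estimate or interval for any effect against control. The rough intervals span both gain and loss for all three active arms in both diaphragm force rows, so p = 0.63 and p = 0.93 should not be read as evidence of no effect.

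The figures rest on quartile-derived SDs, normality (the SAP itself reports outliers), centring on differences in medians, and measured patients only. Other choices of SD and estimator move the limits but not this reading. For change in diaphragm force, a median-type standard error with arm SDs and 1.96 gives upper limits of +1.6, +2.3 and +2.4. Exact limits need patient data. No numerical claim is made for quadriceps.

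**What to change.** Keep the Kruskal-Wallis tests. Whatever the omnibus p, report the three active-minus-control Hodges-Lehmann shifts with confidence intervals for four rows: force after treatment and change in force, for diaphragm and for quadriceps. Use 98.3% for each interval so that the three in a row are nominally simultaneous. Label the estimates post hoc, because the results are already in hand. State beside them that they describe only patients with the measurement (44 of 73 for diaphragm force; 17 + 13 + 11 + 13 = 54 of 73 for quadriceps) and do not bound the effect in all randomised patients. A sentence on whether the Tukey comparisons were run is optional.

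The cost is a wording change and one re-run on existing data. The downsides are 12 extra post hoc estimates (3 contrasts x 4 rows), no expected change in significance, and coverage somewhat below nominal where spreads differ, as in step 7 of the working. The SAP should mention that last limit.
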